9.1.9. Measures Taken to Minimize Bias

9.1.9.1. Randomization

Assessment of eligibility must be done prior to randomization. Suitable subjects will be randomized to procedure with PCI or CABG in a ratio of 1:1. Randomization will be stratified by medically treated diabetes mellitus (diabetic vs. non-diabetic), SYNTAX score (<23 vs. \geq 23) and by center.

The randomization will be managed by a central IVRS randomization. See Section 7.2.12 for randomization details. Once randomized the subject is analyzed as part of the intent-to-treat (ITT) population.

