2.3.1 Primary Endpoint

The primary endpoint is the composite measure of all-cause death, myocardial infarction (MI) or stroke (modified Rankin Scale (mRS) ≥ 1 and increase by ≥ 1 from baseline). measured by the Kaplan-Meier failure rate estimate at 3 years. For the primary analysis of the primary endpoint, this Kaplan-Meier rate will be defined from the date of randomization. All available data through 3-year follow-up will be used, but only events occurring up to day 1095 after randomization will be counted for the primary endpoint. For a sensitivity analysis, the Kaplan-Meier rate will be defined at the time of the index procedure date. Both of these analyses will be conducted at the time when approximately 50% of the patients have reached the 3-year follow-up AND all patients have reached the 2-year follow-up, whichever time point is latest.

For the primary and sensitivity analyses, days from the randomization date and procedure date to the first occurrence of one of the events within this composite, an early withdrawal date, or the last follow-up date will be calculated for each patient respectively. For patients who dropped out early, but had a death date available per the national death registry, this date will be used in the calculation of days (and will be counted as a primary endpoint event). If a patient does not have an event or an early withdrawal date:

- Days from randomization will be set to 1095 days (3 years) if their last follow-up date is known to occur after 3 years.
- The date of the last visit will be the date of the last phone call, office visit or medical contact.

The primary endpoint will first be tested for noninferiority with a margin of 4.2%. The critical value will be generated using the Com-Nougue¹ approach to estimating the Z-statistic with Greenwood's formula for estimating the standard error.

$$Z = \frac{F_{CABG}(T) - F_{PCI}(T) - \delta}{\sqrt{Var(F_{CABG}(T)) + Var(F_{PCI}(T))}}$$

Where, for each treatment group (CABG or PCI):

F(T) = Kaplan Meier estimator of failure at time T

 δ = non-inferiority margin

Var = variance of the estimator = σ^2 , where σ is defined as:

$$\sigma$$
 = standard error by Greenwood's formula = S(T=1095) $\sqrt{\sum_{j=1}^{1095} \frac{d_j}{n_j s_j}}$

S = 1 - F = KM estimate of survival at time T

n = number of subjects

d = number of events

s = n-d

The 95% CI for $F_{CABG}(T) - F_{PCI}(T)$ is then:

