2.8 RANDOMIZATION AND BLINDING

Approximately 1,900 subjects will be enrolled in a 1:1 ratio to either PCI with the XIENCE stent or CABG treatment. Randomization will be stratified by the presence vs. absence of medically treated diabetes, SYNTAX ⁽⁴⁾ score <23 vs. \geq 23, and study center. A centralized randomization service will be used.

Randomization will be performed after informed consent has been obtained and all eligibility criteria have been confirmed. Once randomized, the subject is considered registered in the trial and analyzed as part of ITT population. Once randomization is completed and a treatment is assigned, crossover is not permitted.

This is an unblinded clinical study.

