3.2 Analysis of the Primary Endpoint

The primary analysis for non-inferiority and superiority will use the Kaplan-Meier estimates defined from randomization date. A sensitivity analyses for superiority will also be performed where time is defined from randomization. Additional sensitivity analysis for the same non-inferiority and superiority test mentioned above will be rerun changing the start date from randomization to procedure date. The stop date for all analyses defined at 3 yeatrs will be 1095 days from randomization.

Primary and supplemental analyses are defined below.

- 1. Primary Analysis of the Primary Endpoint for non-inferiority: Code for the primary analysis testing for non-inferiority with 1-sided alpha = 0.025, the non-inferiority margin $\delta = 4.2\%$.
 - Run the product-limit model:

```
Proc lifetest data = DATAXX method = pl cs=none atrisk
```

```
timelist = 1095 outsurv = OUTSURV ;
```

Time Timevar*Censvar(0);

strata/ Group = treatment test = logrank;

Run;

- Use results in OUTSURV to compute formula in 2.3.1. Reject Ho if the critical value $< -Z_{1-\alpha}$
- 2. Primary Analysis of the Primary endpoint using Z test for Superiority: Code for the primary endpoint testing for superiority with 1-sided alpha = 0.025: same as above, only use $\delta = 0$ in calculations. This will be the primary test for superiority.
- 3. Sensitivity Analysis using Cox Model for Superiority: The primary endpoint is tested for superiority with 1-sided alpha = 0.05 using a Cox proportional hazards model. The proportional hazard assumption will first be tested by plotting the log-negative-log survival curves vs the log of survival time for each level of treatment group.

If it is determined that the proportional hazard assumption is violated, then a logistic regression will be performed adjusting for time of follow-up in each group.

Code to Test Proportional Hazard Assumption:

proc lifetest data=DATAXX plot=(lls) noprint; time Timevar*Eventvar(0); strata Group; run; Code for Cox model where Proportion Hazard Assumption is **Not** violated: ods output ParameterEstimates=*Out1*; Proc phreg data = DATAXX ; model Timevar*Eventvar (0) = Group / rl; run;

Summary tables for time to event endpoints will include failure rates (Kaplan-Meier estimates), unadjusted hazard ratios, confidence interval for the hazard ratio, and a p-value.

```
Code for Logistic Regression used when Proportional Hazard Assumption is violated:

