3.3 Analysis of the Powered Secondary Endpoints

- The first powered secondary endpoints, the KM estimate of the composite rate of allcause mortality, MI or stroke (mRS≥1 and increase by ≥1 from baseline) from randomization to 30 days post randomization, will be analyzed in a similar fashion as the primary analysis of the primary endpoint described in Section 3.2 above. The key differences are that a 1-sided alpha is set at 0.05 and only non-inferiority will be tested at a margin of 2%.
- The second powered secondary endpoint is the KM estimate of the composite rate of all cause mortality, MI, stroke (mRS≥1 and increase by ≥1 from baseline) or unplanned revascularization at 3 years. The same analysis will be performed as described for the primary anaylsis of the primary endpoint except the non-inferiority margin = 8.4%

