3.6.1.3 Covariate Adjusted Analysis

A multivariable Cox model (or logistic regression if the proportional hazards assumption is not met) will be performed, adjusting for baseline variables historically known to be prognostically important in order to identify independent correlates for the outcomes of interest, as follows (number of variables selected to avoid model over-fitting; i.e. ~1 variable for every 10 events based on the anticipated rates):

Outomce = All-cause death/MI/stroke up to 30 day:

• age, gender, diabetes, LVEF, SYNTAX score groups (core lab), randomization arm (forced in)

Outcome= All-cause death/MI/stroke up to 3-year:

• age, gender, diabetes, hypertension, hyperlipidemia, prior MI, current smoking, prior cerebrovascular disease, prior PAD, prior heart failure, prior COPD, presentation in ACS vs stable CAD, baseline anemia, baseline creatinine clearance, LVEF, SYNTAX score groups (core lab), randomization arm (forced in)

Outcome= All-cause death/MI/stroke/unplanned revascularization up to 3-year:

• same as all all-cause death/MI/stroke

Continuous data such as age will be entered as continuous except as otherwise noted.

For Syntax score groups: <23, 23-32, >32, two dummy variables will need to be created:

If Syntax score < 23 then Syntax23=1; Else if Syntax ne . then Syntax23 = 0; If Syntax score > 32 then Syntax32=1; Else if Syntax ne . then Syntax32 = 0; Add both of the above dummy variables to the model in place of the 3 way Syntax I score.

Appropriate methods may be used to impute missing baseline values.

1). Test the proportional hazard assumption:

The proportional hazard assumption will first be tested by plotting the log-negative-log survival curves vs the log of survival time for each level of treatment group against each covariate one at a time.

Code to Test Proportional Hazard Assumption: proc lifetest data=DATAXX plot=(lls) noprint; time Timevar*Eventvar(0); strata Covariate; run:

2). If it is determined that the proportional hazard assumption is NOT violated then a Cox regression model will be performed with a stepwise option.

Code for Cox model where Proportion Hazard Assumption is **Not** violated: Proc phreg data=infile; Model timevar*Eventvar(0)=group *baselinevars*; Run;

Summary tables from this model will include failure rates (Kaplan-Meier estimates), adjusted hazard ratios, confidence interval for the hazard ratio, and a p-value.

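### Free improvement: the confirmatory primary test ignores the diabetes and SYNTAX strata used in randomisation, at a cost of roughly 0.1 to 1.3 power points

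*SAP*

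**What the plan says.** SAP 2.8 says: "Randomization will be stratified by the presence vs. absence of medically treated diabetes", then adds SYNTAX score and study center. Protocol 9.1.9.1 lists the same factors, ending with "SYNTAX score (<23 vs. \geq 23) and by center". Protocol 7.2.12 shows that the coordinator gives the IVRS the SYNTAX score and diabetes status before allocation.

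The analysis does not use these factors:

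- SAP 2.3.1, on the primary test: "The critical value will be generated using the Com-Nougue" approach. The Z statistic divides the difference of two arm-level Kaplan-Meier rates by the root of the summed Greenwood variances. No stratum index appears.
- SAP 3.2, code for that test: "strata/ Group = treatment test = logrank". No variable stands before the slash.
- SAP 3.2, Cox sensitivity model: "model Timevar*Eventvar (0) = Group / rl", with tables that report "unadjusted hazard ratios, confidence interval for the hazard ratio, and a p-value".
- SAP 3.3, first powered secondary endpoint: it "will be analyzed in a similar fashion as the primary analysis of the primary endpoint described in Section 3.2 above". The second is also given the method of the primary analysis.

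Diabetes and SYNTAX enter only the descriptive subgroup models (SAP 3.5) and the exploratory covariate-adjusted model (SAP 3.6.1.3). Neither document says why the confirmatory tests are unstratified.

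**The concern.** When randomisation balances the arms on prognostic factors, the between-stratum part of the outcome variance largely drops out of the treatment difference. An unstratified standard error still counts it. The standard error is then slightly too large, the test slightly conservative, and some power is given away. SAP 3.6.1.3 lists diabetes and SYNTAX among variables historically known to be prognostic, which is the condition under which this matters. The trial is planned at only about 80% power, and both factors are recorded before allocation, so even a small gain is worth having if it is free.

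**Working it through.** **Inputs from SAP 2.5.1:** 11% event rate per arm at 3 years, margin 4.2 points, one-sided alpha 0.025, 950 per arm, 8% loss.

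**Stated power.** Effective n = 950 × 0.92 = 874 per arm.
SE = √(2 × 0.11 × 0.89 / 874) = 0.01497.
Power = Φ(0.042/0.01497 − 1.960) = Φ(0.846) = 80.1%, against the stated approximate 80%. The required n is 872 per arm, and 872/0.92 = 948, against 950. The plan's figure reproduces.

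**Effect of stratifying.** Let f be the between-stratum variance of the event rate divided by p(1 − p) = 0.0979. The stratified SE is 0.01497 × √(1 − f). Prevalences and risk ratios are assumptions, because the documents give none for the randomised population.

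Worked case: 30% diabetic with ratio 1.5, and 40% SYNTAX 23 or more with ratio 1.5.

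- Reference rate = 0.11/(1.15 × 1.20) = 0.0797.
- Cell rates 0.0797, 0.1196, 0.1196, 0.1793, with weights 0.42, 0.28, 0.18, 0.12.
- Between-stratum variance = 0.42 × 0.0303² + 0.46 × 0.0096² + 0.12 × 0.0693² = 0.0010, so f = 1.03%.
- Stratified SE = 0.01489. Power = Φ(2.8205 − 1.960) = 80.5%.
- Size of the unstratified test under perfect balance = Φ(−1.960/√0.9897) = 2.44%.

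| Diabetic, ratio | SYNTAX 23 or more, ratio | f | Stratified power | Unstratified one-sided size |
|---|---|---|---|---|
| 25%, 1.25 | 40%, 1.10 | 0.16% | 80.2% | 2.49% |
| 30%, 1.20 | 40%, 1.16 | 0.16% | 80.2% | 2.49% |
| 30%, 1.50 | 40%, 1.16 | 0.56% | 80.3% | 2.47% |
| 30%, 1.50 | 40%, 1.50 | 1.03% | 80.5% | 2.44% |
| 30%, 2.00 | 40%, 1.50 | 2.1% | 81.0% | 2.38% |
| 35%, 2.00 | 50%, 2.00 | 3.1% | 81.3% | 2.32% |
| 30%, 2.00 | 40%, 2.00 | 3.2% | 81.4% | 2.32% |

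The second row takes its ratios from the protocol. In the single-arm left main study (Protocol 2.7.2), one-year event-free survival was 90% and 88.4% in the two lower SYNTAX groups: 11.6/10 = 1.16. In the single-arm stent study (Protocol 2.7.4), one-year target lesion failure was 5.73% with diabetes and 4.80% without: 5.73/4.80 = 1.19. Endpoint and time point differ from this trial's, so these are only a guide.

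**What the gain is measured against.** The table compares with the planning figure of 80.1%. If balance were perfect, the unstratified estimate would already have the smaller spread, and only the critical value would be too strict. In the last row its power would be Φ((0.042 − 1.960 × 0.01497)/0.01472) = Φ(0.860) = 80.5%, so the gain would be 0.9 points, not 1.3.

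**Balance actually achieved.** About 165 centres × 4 cells = 660 cells, or 1,900/660 = 2.9 patients per cell. Block size is not stated, so many blocks may stay incomplete. The sizes in the last column assume perfect balance and are therefore the extreme. A simulation that added centre as a stratum was too noisy to settle how much conservatism remains.

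**Heavier censoring.** With administrative censoring (2-year minimum, 29-month accrual) in the Greenwood variance, base power is 77.8%. Over the first to the sixth row without the second and third, stratifying gives 77.8% to 79.0%, a similar gain.

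**Powered secondary endpoints.** At 30 days, f is at most 0.8% and power moves from 81.9% to at most 82.1%. In the worked case the diabetic, high-SYNTAX cell would have 950 × 0.12 × (0.03 × 2.25/1.38) = 5.6 expected events per arm. For the 3-year composite with revascularisation, f reaches 7.1%, but power moves only from 99.3% to 99.5%.

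**The case against.** The strongest reply is that the effect is trivial and on the safe side. The SAP states power only as approximate and accepts a difference of up to 0.5% between two power methods, and the low rows fall inside that tolerance. This stands, and it is why the point is only an improvement.

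It also stands that the size rests on assumed inputs. The upper end needs both risk ratios at 2.0. The steep SYNTAX gradient in the protocol's background appears at scores of 33 or more, which the trial excludes.

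A further reply is that adjustment is already planned. The list in SAP 3.6.1.3 includes diabetes and "SYNTAX score groups (core lab), randomization arm (forced in"). That model is exploratory and stepwise, and it uses three core-laboratory SYNTAX groups, whereas randomisation used the score supplied by the site, cut at 23. It does not replace a stratified confirmatory test. The difference between site and core-laboratory scores does mean that the prognostic strength of the stratum as entered could be weaker than assumed.

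A reader might infer that an analysis ignoring the strata is invalid or inflates type I error. The documents do not support that: pooling over balanced strata makes the standard error too large, if anything, and the stated alpha is protected.

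**Conclusion.** The observation holds as a free improvement. The confirmatory primary test and the Cox sensitivity model ignore the stratification factors without explanation. The variance of the primary difference could fall by about 0.2-3%, and power could rise by about 0.1-1.3 points from 80.1%. This assumes 25-35% diabetic, 40-50% SYNTAX 23 or more, and risk ratios of about 1.1 to 2.0. The low end agrees better with the protocol's one-year contrasts. If neither factor is prognostic, the gain is zero. The conservatism may be smaller than the table shows, because centre is a third stratum with very small cells.

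Two stronger readings should be resisted. One is that the trial is materially underpowered for this reason; a gain of at most about 1.3 points does not show that. The other is that all powered endpoints need stratified tests; for the secondary endpoints the gain is at most about 0.3 points, and the 30-day strata would hold few events.

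**What to change.** In SAP 3.2, for the primary endpoint:

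1. Estimate the 3-year Kaplan-Meier difference within each of the four strata formed by medically treated diabetes and SYNTAX below 23 versus 23 or more, using the values entered in the IVRS.
2. Combine the four differences with weights equal to each stratum's share of the ITT population. This keeps a marginal 3-year risk difference, so the 4.2% margin keeps its meaning.
3. Take the standard error as the root of the sum of squared weights times the stratum Greenwood variances of the two arms.
4. Keep the present unstratified test as a named sensitivity analysis.
5. Add the two factors in a STRATA statement to the Cox sensitivity model.

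Leave centre out, because its cells are too small. In the worked case the smallest stratum has about 950 × 0.12 = 114 patients per arm and about 114 × 0.179 = 20 events, enough for stratum-level estimates. Stratifying the powered secondary endpoints is optional.

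The cost is SAP wording and code, with no new data. Protocol 5.1, 9.1.1 and 9.1.6.1 describe the Kaplan-Meier difference or its Greenwood standard error and should be aligned. If the team prefers the unstratified test, one sentence giving the reason, with the stratified version as a sensitivity analysis, would be enough.

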3 ANALYSIS CONSIDERATIONS

3.1 GENERAL STATISTICAL METHODS

Baseline demographic, clinical, angiographic, procedural and device data, and treatment results will be summarized using descriptive summary statistics. All data collected will be summarized overall and by treatment arms.

3.2 Analysis of the Primary Endpoint

The primary analysis for non-inferiority and superiority will use the Kaplan-Meier estimates defined from randomization date. A sensitivity analyses for superiority will also be performed where time is defined from randomization. Additional sensitivity analysis for the same non-inferiority and superiority test mentioned above will be rerun changing the start date from randomization to procedure date. The stop date for all analyses defined at 3 yeatrs will be 1095 days from randomization.

Primary and supplemental analyses are defined below.

- 1. Primary Analysis of the Primary Endpoint for non-inferiority: Code for the primary analysis testing for non-inferiority with 1-sided alpha = 0.025, the non-inferiority margin $\delta = 4.2\%$.
 - Run the product-limit model:

```
Proc lifetest data = DATAXX method = pl cs=none atrisk
```

```
timelist = 1095 outsurv = OUTSURV ;
```

Time Timevar*Censvar(0);

strata/ Group = treatment test = logrank;

Run;

- Use results in OUTSURV to compute formula in 2.3.1. Reject Ho if the critical value $< -Z_{1-\alpha}$
- 2. Primary Analysis of the Primary endpoint using Z test for Superiority: Code for the primary endpoint testing for superiority with 1-sided alpha = 0.025: same as above, only use $\delta = 0$ in calculations. This will be the primary test for superiority.
- 3. Sensitivity Analysis using Cox Model for Superiority: The primary endpoint is tested for superiority with 1-sided alpha = 0.05 using a Cox proportional hazards model. The proportional hazard assumption will first be tested by plotting the log-negative-log survival curves vs the log of survival time for each level of treatment group.

If it is determined that the proportional hazard assumption is violated, then a logistic regression will be performed adjusting for time of follow-up in each group.

Code to Test Proportional Hazard Assumption:

proc lifetest data=DATAXX plot=(lls) noprint; time Timevar*Eventvar(0); strata Group; run; Code for Cox model where Proportion Hazard Assumption is **Not** violated: ods output ParameterEstimates=*Out1*; Proc phreg data = DATAXX ; model Timevar*Eventvar (0) = Group / rl; run;

Summary tables for time to event endpoints will include failure rates (Kaplan-Meier estimates), unadjusted hazard ratios, confidence interval for the hazard ratio, and a p-value.

```
Code for Logistic Regression used when Proportional Hazard Assumption is violated:

proc logistic data= DATAXX descending;

class Group;

model Event (event=1) =TimeVar Group / rl;

run;

Where Event = all first events from randomization or procedure date to 1095 days

Timevar = Days from Randomization or procedure date to last data point

available for patient while on study. If the patient did not drop

out prior to the analysis time point then this will be set to the

analysis time point.
```

The odds ratio, 95% confidence interval of the odds ratio and p-value will be presented from this logistic model

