9.1. Randomized Cohort

9.1.1. Primary Endpoint

The primary endpoint is a composite of all-cause mortality, MI or stroke (mRS \geq 1 and increase by \geq 1 from baseline) at 3 years post randomization. The primary endpoint will be estimated via Kaplan-Meier failure rate measured from randomization and Greenwood's formula for estimating the standard error. The primary endpoint analysis will be conducted at the time when approximately 50% of the patients have reached the 3-year follow-up AND all patients have reached the 2-year follow-up, whichever time point is latest. All available data through 3-year follow-up will be used.

The analysis will also be performed at 3 years post index procedure, as a sensitivity analysis.

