2.3.2 Major Secondary Endpoints

The primary analysis for these two powered secondary endpoints will be based on the analysis applied to the time from randomization estimate. Sensitivity analyses will be performed on the time from procedure estimate. There are two major powered secondary endpoints:

- Composite measure of all-cause mortality, MI or stroke (mRS≥1 and increase by ≥1 from baseline) presented as a Kaplan Meier rate defined from randomization to 30 days post randomization This is the same as the primary endpoint measured at 30 days. Two sets of analyses will be performed. Days from the randomization date or procedure date to the first occurrence of the one of the events within this composite, an early withdrawal date, or the last follow-up date will be calculated for each patient respectively. For patients who dropped out early, but had a death date available per the national death registry, this date will be used in the calculation of days (and will be counted as an event). If a patient does not have an event or an early withdrawal date then days from randomization will be set to 30 days if their last follow-up date is known to occur after 30 days. These KM estimates will be put into the Z statistic defined in Section 2.3.1 using a margin of 2% to test for non-inferiority.
- Composite measure of all-cause mortality, MI, stroke (mRS≥1 and increase by ≥1 from baseline), or unplanned revascularization for ischemia occurring from the time of randomization up to study day 1095, as estimated by the Kaplan-Meier failure rate and analyzed using a Z statistic in the same way it is described under the Section 2.3.1, with a 1-sided alpha of 0.05 and a margin of 8.4%. All available data through 3-years of follow-up will be used. Days from the randomization date or the procedure date to the first occurrence of one of the events within this composite, an early withdrawal date, or the last follow-up date occurring by 3 years post randomization will be calculated for each patient. For patients

who dropped out early, but had a death date available per the national death registry, this date will be used in the calculation of days and counted as an event. If a patient does not have an event or an early withdrawal date:

- Days from randomization will be set to 1095 days (3 years) if their last follow-up date is known to occur after 3 years.
- The date of the last visit will be the date of the phone call, office visit or last medical contact.

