3.4.3 Time to Event Variables

Survival analysis techniques will be used to analyze the time-to-event variables that occur at or after 30 days of follow-up. All of these analyses will be performed with time defined from date of randomization and from date of procedure. Subjects without events will be censored at their last known event-free time point. If this event-free time point occurs after the analysis time point, the days to event variable will be set equal to the analysis time point so that the patient will be included in the analysis (e.g. if the last data point was collected at 3 years and 1 week post randomization, for the 3 year analysis, this patient is censored at exactly 3 years [1095 days]). For patients who did not have an event or early withdrawal and have not yet completed the 3 year visit, they will be censored at the time of their last follow-up. Time to first event curves will be constructed using Kaplan-Meier estimates.

For time to event variables such as MI, stroke and and revascularization, at all post discharge results will be summarized with Kaplan-Meier estimates of event rates. For time to event variables such as death and composite endpoints including death, deaths will be included for patients who dropped out early, but had a known death date, prior to study day 1095, from the national death registry.

For time to event analyses, hazard ratios, confidence interval for the hazard ratios, and p-values may also be presented from a Cox proportional hazards model.

Formulas are given below. Please note that in using these formulas, it is assumed that the data are independent observations.

The Kaplan-Meier product-limit estimator is defined as follows:

$$\hat{S}(T) = \begin{cases} 1 & \text{if } T_{\min} > T \\ \prod_{A \le T_i \le T} \left[1 - \frac{d_i}{r_i} \right] & \text{if } T_{\min} \le T. \end{cases}$$

The variance of S(T) is estimated by Greenwood's formula where

$$\hat{V}\left[\hat{S}(T)\right] = \hat{S}(T)^2 \sum_{A \le Ti \le T} \frac{d_i}{r_i(r_i - d_i)}$$

The Kaplan-Meier failure rate estimator and it's variance are defined as

$$\hat{F}(T) = 1 - \hat{S}(T)$$
$$\hat{V}[\hat{F}(T)] = \hat{V}[\hat{S}(T)]$$

 $100(1-\alpha)$ % Confidence Interval for the hazard ratio

Cox proportional hazards regression will be used to obtain the confidence interval for the hazard ratio. The phreg procedure in SAS will be used to obtain the Wald confidence limits. An example of the code is as follows:

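### The procedure-date sensitivity analysis starts its clock at the index procedure but stops at 1095 days from randomization, so it does not match the 3-year post-procedure analysis in the protocol

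*SAP*

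**What the plan says.** Protocol 9.1.1, after defining the primary endpoint from randomization, adds: "The analysis will also be performed at 3 years post index procedure, as a sensitivity analysis". The horizon is on the procedure clock.

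SAP 3.2 provides for the same non-inferiority and superiority tests to be "rerun changing the start date from randomization to procedure date". Its next sentence fixes the end of the window for every 3-year analysis: "The stop date for all analyses defined at 3 yeatrs will be 1095 days from randomization". It makes no exception for the rerun just described. The only Kaplan-Meier code shown is for the randomization-based primary analysis and reads the estimate at day 1095 ("timelist = 1095 outsurv = OUTSURV"). No separate procedure-date code is given.

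Other parts of the SAP point in different directions:

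- The logistic fallback in SAP 3.2 defines "Event = all first events from randomization or procedure date to 1095 days", which is a 1095-day window on whichever clock is in use.
- SAP 3.4.3 covers both time origins and says that, for patients known to be event-free beyond the analysis time point, "the days to event variable will be set equal to the analysis time point". It sits under the non-powered secondary endpoints, and its only worked example is timed from randomization.
- SAP 2.3.2 counts days from randomization or procedure for the second major secondary endpoint, but bounds them by "the last follow-up date occurring by 3 years post randomization".
- SAP 2.3.1 says how days from randomization are set for event-free patients and has no matching rule for days from procedure.

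SAP Section 5, which lists changes from the protocol, does not mention a change to this window.

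**The concern.** The origin and the stop date are on different clocks. The analysis that the protocol names, an event rate 3 years after the procedure, is not the one that SAP 3.2 specifies. Under the SAP rule each patient's maximum post-procedure observation time is shortened by that patient's own wait for treatment. If waits differ between arms, the two Kaplan-Meier curves end at different post-procedure days, and the last stretch of each rests on a rapidly shrinking risk set.

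The stakes are limited to a pre-specified sensitivity analysis: which data enter it, and whether its result can be described as a 3-year post-procedure comparison.

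**Working it through.** **The plan's own figure.** The rerun uses the primary test, so its sample size comes first. The inputs, from SAP 2.5.1, are 11% in each arm, margin 4.2%, one-sided alpha 0.025, 80% power and 8% loss.

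n = (1.960 + 0.842)² × 2 × 0.11 × 0.89 / 0.042² ≈ 872 per arm; 872 / 0.92 ≈ 948. The SAP states 950, so the figure is reproduced.

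**Limits on the gap g from randomization to procedure.** Protocol 8.2 allows the procedure on the randomization date (g = 0). Protocol 4.3 requires revascularization within 2 weeks. The per-protocol set in SAP 2.4.2 accepts up to 4 weeks. Protocol 6.6 and 20.1.3 describe randomization in the catheterization laboratory followed directly by PCI. Protocol 7.2.3 has CABG postponed by at least 5 or 7 days in stable subjects taking an ADP antagonist. Neither document gives a distribution of g by arm.

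**Last observable post-procedure day under SAP 3.2** is 1095 − g. With a constant hazard giving 11% at day 1095, F(t) = 1 − 0.89^(t/1095), and the shortfall is 11% − F(1095 − g):

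| Gap g (days) | Last post-procedure day | Shortfall (points) |
|---|---|---|
| 1 | 1094 | 0.01 |
| 7 | 1088 | 0.07 |
| 14 | 1081 | 0.13 |
| 28 | 1067 | 0.27 |

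The 14-day shortfall is 0.13 / 4.2 ≈ 3% of the margin.

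**Numbers at risk and precision.** These come from simulation with 950 per arm, an 11% 3-year rate, uniform accrual over 29 months, analysis 758 days after the last entry, 8% loss and assumed gap distributions.

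- Stop at 1095 days after the procedure: about 475 per arm at risk at post-procedure day 1095; standard error of the difference about 1.53 points.
- Stop as written: about 30 to 120 PCI patients at risk at that day, depending on the assumed same-day share, and 0 to 5 CABG patients, with 0 whenever no same-day CABG is assumed. The typical standard error is about 1.54 to 1.55 points if the last value is carried forward.
- At post-procedure day 1081, with gaps of at most 14 days, about 485 to 490 per arm are at risk under either rule.

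**Effect on the test.** When both rules are applied to the same simulated trials, carrying the last value forward costs about 1 to 1.5 points of power, from about 77%, and changes the non-inferiority call in 2 to 5% of trials. Separate sets of 400 trials per rule cannot resolve this: the Monte Carlo error of each pass rate is √(0.77 × 0.23 / 400) ≈ 2.1 points. Such runs gave 77–81% as written and 74–77% with the procedure-based stop, a difference that should not be read as real.

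**The case against.** The strongest reply is that nothing of substance is lost. Kaplan-Meier and Greenwood quantities are sums over event times, so the difference, its standard error and Z exist up to the last patient at risk, within about two weeks of the nominal time. The shortfall is a small fraction of the margin. That stands. A reader might infer from the mismatch that the comparison cannot be computed, but the documents do not support this. Only the value at exactly day 1095 is undefined or carried forward, and only in an arm with no same-day procedures.

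Three further inferences also go too far:

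- That no CABG patient can be at risk at day 1095. This rests on an assumed minimum delay. Protocol 8.2 does not limit same-day procedures to PCI, and the 5- or 7-day wait applies only to stable subjects already on an ADP antagonist. PCI patients with a gap are truncated in the same way.
- That the rule ends patient follow-up. It limits an analysis window; Protocol 4.2 follows randomized subjects for at least five years after the procedure.
- That the analysis was designed to test whether unequal waiting drives the result. The documents call it only a sensitivity analysis.

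There is also a reason for the randomization-based stop. The adverse event check (Protocol 4.2 and 8.2, SAP 2.3) is meant to secure data equally in both arms to day 1095 from randomization, and patients already seen at day 1067 or later need no further contact. Later data may be less complete. This is a fair caution about the fix, but it does not reconcile the SAP with the protocol or with its own logistic fallback.

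**Conclusion.** The mismatch is real and minor. Protocol 9.1.1 sets the horizon at 3 years after the procedure. SAP 3.2 pairs a procedure-date start with a randomization-based stop, and the logistic fallback in the same section says otherwise. Under the stop rule as written, only same-day procedures can contribute at post-procedure day 1095. That the arm left without such patients would be CABG is probable but an inference, because the gap distribution is not given.

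The effect is about 0.13 points of event rate for a 14-day gap and about 1 to 1.5 points of power. The first figure assumes a constant hazard; the second also depends on the assumed gaps, uniform accrual and carrying the last value forward. The primary analysis, its margin, its alpha and the definition of study success do not change. The 30-day endpoint is not affected either, because the stop rule quoted covers only analyses defined at 3 years.

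**What to change.** In SAP 3.2, state that for 3-year analyses timed from the index procedure the stop date is 1095 days after the procedure, using available later follow-up and censoring at last contact. State that the stop at 1095 days from randomization applies only to randomization-based analyses. Align SAP 2.3.1 (adding a rule for days from procedure), 2.3.2 and 3.4.3 with this wording.

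The cost is one sentence, the matching edits and one date variable in the program. The snapshot must keep events and contacts shortly after day 1095 from randomization. The drawback is that the adverse event check equalises ascertainment only to that day, so the last days on the procedure clock may be less complete.

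If that is a concern, read both arms at one earlier common post-procedure day. Day 1081 (1095 − 14) can be reached by every patient treated within the 2-week limit, even under the present stop date. That choice departs from the protocol's 3-year horizon and should be listed in SAP Section 5. Either rule should be fixed before the database snapshot.
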